Endpoints	
Primary endpoint:
 
 ➤ Rate of response at 6 weeks after switching from rhTPO to eltrombopag or vice versa 
Response is defined according to the Chinese guidelines for treatment of adult primary immune thrombocytopenia as ⁷:
 
Complete response (CR): platelet count $\geq 100 \times 10^9/L$ and absence of bleeding.
 
Response (R): platelet count range $30-100 \times 10^9/L$, at least doubling of the baseline count, and absence of bleeding.
 
No response (NR): platelet count $< 30 \times 10^9/L$, or less than doubling of the baseline count, or bleeding.
 
The rate of response at 6 weeks includes the total proportion of patients who achieved CR and R at 6 weeks in the groups switch from rhTPO to eltrombopag and eltrombopag to rhTPO, respectively.
 
Secondary endpoints:
 
 ➤ Rate of response at 6 weeks after switching, according to the reasons of switching 
The reasons of switching include ³:
 
Lack of efficacy:
 
 -1st TPO-RA failure: no response to either one TPO-RA administered before switch -Loss of response: relapsed after transient response to 1st TPO-RA (relapse is defined as platelet count $< 30 \times 10^9/L$, or less than doubling of the baseline count, or bleeding, after the achievement of CR or R. The blood platelet count should be confirmed on at least two separate occasions, which is at least 1 day apart when used to define relapse ⁷) 
Platelet count fluctuations: unstable platelet counts necessitating rescue therapy or transient TPO-RA dose modifications/withdrawal with associated risk of either rebound thrombocytopenia/bleeding or thrombocytosis
 
Patient's preference
 
Development of adverse events necessitating 1st TPO-RA discontinuation
 
 ➤ Proportion of patients who achieved, regained, and maintained response at 6 weeks after switching 
Response achieved refers to patients who failed the 1st TPO-RA achieve CR or R at 6 weeks after switching.
 
Response regained refers to patients who lost response to the 1st TPO-RA achieve

CR or R at 6 weeks after switching.

Response maintained refers to patients who achieved CR or R with the 1st TPO-RA and still respond to the 2nd TPO-RA at 6 weeks after switching.

- Rate of response at 3 months after switching from rhTPO to eltrombopag or vice versa

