- Rate of response at 3 months after switching, according to the reasons of switching
- Proportion of patients who achieved, regained, and maintained response at 3 months after switching
- Time to response from 1st TPO-RA switching for patients who switch due to lack of efficacy
- Duration of response from 1st TPO-RA switching for patients who switch due to lack of efficacy

Duration of response is defined as the time from when CR or R is achieved/regained to the time of relapse.

- Proportion of patients with any bleeding (WHO bleeding scale grade 1–4¹¹) and clinically significant bleeding (WHO bleeding scale grade 2–4¹¹)
- Total score of bleeding calculated according to the Bleeding Rating System⁷
- Patient and physician's treatment preference

At 6 weeks after switching, patients will be asked whether they prefer to continue treatment with rhTPO or eltrombopag, or whether they had no preference¹². In addition, patients who prefer one TPO-RA over the other will be queried on the reasons of preference (Patient preference questionnaire attached as Appendix 1).

At 6 weeks after switching, physicians will also be asked whether they prefer to further treat the patient with rhTPO or eltrombopag, or whether they had no preference, taking into account the patient's preference, response, and tolerability¹².

At 3 months after switching, the measurement will be applied again.

- Safety of treatment

The safety of treatment will be determined from adverse events summarized by incidence and severity, and from clinical laboratory evaluations, physical examinations and ophthalmological examinations carried out during scheduled study visits.

Exploratory endpoints:

- Association between clinical characteristics and response after switching

The following clinical characteristics will be compared between responders and non-responders at 6 weeks and 3-month after switching, respectively: gender (male vs female), age at 1st TPO-RA, time from diagnosis to 1st TPO-RA, lines of previous therapy before 1st TPO-RA, maximum 1st TPO-RA dose received vs. not received, splenectomy status (yes vs no), switch sequence (rhTPO to eltrombopag or vice versa), switching behavior, switch due to efficacy vs non-efficacy issues, and 1st TPO-RA failure vs loss of response.

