	
3 months after switching.
 
The observation period is 3-month for each patient enrolled. Response to 2nd TPO-RA will be assessed throughout the observation period with response at 6 weeks being the primary evaluation. Adverse events, including bleeding events, will be assessed and recorded together with concomitant ITP treatment. Preference of patients and doctors on the two TPO-RAs will also be assessed.

Investigational Drug Administration	
Patients will initiate eltrombopag treatment with a dose of 50 mg once daily. Dose adjustment of study medication will be allowed to maintain platelet counts between 50*10⁹/L and 250*10⁹/L.
 
Patients will initiate rh-TPO with a dose of 300 U/kg/d for \leq14d. Patients who attained stable PLT counts (\geq50*10⁹/L) in two consecutive tests will enter maintenance therapy, starting with every other day administration of rhTPO, then adjust dose interval to maintain platelet counts at 30-100*10⁹/L.

Dose Adjustment Guidelines	
The following information serves as a reference; actual dose adjustment will be conducted according to clinical practice in considering the medical condition of a patient:
 
Eltrombopag: refer to Table 2.
 
RhTPO:
 
At initial treatment, rhTPO will be suspended when platelet counts \geq100*10⁹/L. During maintenance therapy, patients with platelet counts $>$150*10⁹/L will suspend treatment until platelet counts drop to \leq150*10⁹/L. Dosing interval will be prolonged when platelet count is \geq100*10⁹/L to \leq150*10⁹/L. Dose modification is not required when platelet count is \geq30*10⁹/L to $<$100*10⁹/L¹³.

Patient Population	Chinese adult patients with primary immune thrombocytopenia who failed first-line corticosteroid therapy and received rhTPO and then switch to eltrombopag or vice versa.
Key Inclusion Criteria	
 • Age 18 years or older • Chinese ethnicity • Primary ITP diagnosed according to the current definitions ^{7, 8, 14, 15} • Failed initial glucocorticosteroid treatment, • Applying rhTPO or Eltrombopag as subsequent treatment • Switch from rh-TPO to eltrombopag or vice versa • Treatment on rhTPO for 14 days minimum or Eltrombopag for 4 weeks minimum, if the reason of switching is lack of efficacy or platelet count fluctuations • Available follow-up at least 6 weeks after switching

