Statistical Analysis	
Statistical analysis methods:
 
Statistical analysis will be conducted by SAS Version 9.2 or above. Descriptive statistics for continuous variables include minimum, maximum, mean ± standard deviation and median with inter-quartile ranges (IQR). Categorical variables will be described as frequencies and percentages. Percentage will be calculated based on non-missing data unless otherwise specified. Comparison between categorical variables will be performed using chi-square test or Fisher's exact test, while comparison between continuous variables will be performed using two-sample t test for parametric data and Wilcoxon rank sum test for non-parametric data. Logistic regression will be used to assess the association between clinical characteristics and outcome of response. Time-to-event data will be described by Kaplan-Meier survival curve with log-rank test for between-group comparison.
 
Unless specified, statistical testing will be carried out bilaterally with significance level alpha=0.05, i.e. a p-value of less than or equal to 0.05 will be considered as statistically significant. Methods of descriptive analysis and hypothesis testing will be selected according to the data characteristics. Transformations will be undertaken as needed.
 
Analysis sets:
 
Full Analysis Set (FAS): includes all patients who receive at least one dose of the 2nd TPO-RA and have response assessed at 6 weeks after switching
 
Safety Set (SS): includes all patients who receive at least one dose of the 2nd TPO-RA after switching.
 
Efficacy analysis will be conducted on FAS and safety analysis on SS.

Table 1 Time and Events

Study procedures	Screening	During Treatment				Safety follow-up after treatment suspension/stop	End-of-study Visit
Visit schedule	-14~1d	Every week \pm 3d	Every 2 weeks	Every 4 weeks	Every 8 weeks	Every week \pm 3d	12 weeks \pm 7d

			±3d	±4d	±4d		
Written informed consent	X						
Demographics	X						
Medical history	X						
Physical examination	X	X				X	X
Ophthalmologic examination	X						X
CBC (incl. platelet count)	X	X ^{a, b}		X ^b		X ^e	X
Peripheral blood smear	X						
Liver function tests (ALT, AST, TB)	X		X ^c	X ^c		X ^d	X
Other clinical chemistry (incl. Cr)	X						X
Coagulation tests	X				X		X
Thyroid function test	X						
HBV, HCV, HIV testing	X						
ECG	X						
Ultrasound (spleen)	X				X		X
Chest X-ray	X						
Bleeding assessment	X	X				X	X

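### The only efficacy set requires a 6-week response assessment, so dosed patients without one leave the primary rate, and the 3-month rate even if seen at 3 months, with no missing-data rule or bounds

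*Combined protocol and SAP*

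**What the plan says.** All references are to the combined protocol and SAP.

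- **Statistical Analysis, Analysis sets.** The Full Analysis Set (FAS) is defined as one that "includes all patients who receive at least one dose of the 2nd TPO-RA and have response assessed at 6 weeks after switching". The Safety Set (SS) "includes all patients who receive at least one dose of the 2nd TPO-RA after switching". The two sets differ only in the 6-week condition. Their use is then fixed: "Efficacy analysis will be conducted on FAS and safety analysis on SS".
- **Statistical Analysis, methods.** "Percentage will be calculated based on non-missing data unless otherwise specified". Nothing else is specified for the response rates.
- **Endpoints.** The primary endpoint is the share with CR or R at 6 weeks, given separately for each switch sequence. The three categories (CR, R, NR) are defined by an observed platelet count and bleeding; R, for example, needs "at least doubling of the baseline count". None of them covers a patient who was not assessed. The secondary endpoints include "Rate of response at 3 months after switching from rhTPO to eltrombopag or vice versa", and time to response and duration of response for patients who switched for lack of efficacy.
- **Trial Design.** "Response to 2nd TPO-RA will be assessed throughout the observation period with response at 6 weeks being the primary evaluation". An end-of-study visit at 3 months is planned for all patients. Platelet counts continue at least weekly in patients who suspend or stop the second drug.
- **Sample Size Justification.** The aim is to describe a response rate, not to compare the sequences. The plan expects about 70% response and 20% drop-out, with 100 patients, about 50 per sequence.

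The only additional analysis planned for response concerns rescue medication.

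**The concern.** A set labelled full that admits a patient only once the outcome has been observed is a complete-case set. In a randomised comparison, some of the resulting error might cancel between arms. Here each sequence yields one proportion with no comparator, so any difference in response between assessed and unassessed patients passes straight into the reported figure. The filter also reaches every other efficacy result run on the FAS: response by reason for switching, and the achieved, regained and maintained proportions.

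The 3-month rate raises a separate problem. A patient who was not assessed at 6 weeks but attends the 3-month visit has a known 3-month outcome, and the set definition discards it. The time-to-event endpoints lose information in the same way: follow-up before week 6 could enter a Kaplan-Meier analysis as an event or as censored time, but the patient is removed altogether.

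**Working it through.** **Inputs from the plan.** Expected response 70%; drop-out 20%; 100 patients, about 50 per sequence (Sample Size Justification).

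**The plan's own figure.** 80 / (1 − 0.20) = 100, which reproduces the planned enrolment. The plan therefore expects loss. It does not say when the loss occurs, or whether it is all among dosed patients.

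**Inputs not in the plan.** The share *m* of dosed patients without a 6-week assessment, and the response rate *q* among them. *m* is varied below and *q* runs over its whole range, 0 to 1.

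**Formulas**, with an FAS rate of 0.70:

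- All-dosed rate = 0.70(1 − m) + qm
- Error of the FAS rate = 0.70 − all-dosed rate = m(0.70 − q)
- 95% sampling half-width per sequence, 50 dosed = 1.96 × √(0.21 / (50(1 − m)))

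| m | All-dosed rate, q = 0 to q = 1 | Error of FAS rate (points) | Half-width (points) | Largest error / half-width |
|---|---|---|---|---|
| 5% | 66.5% to 71.5% | +3.5 to −1.5 | 13.0 | 0.27 |
| 10% | 63% to 73% | +7 to −3 | 13.4 | 0.52 |
| 20% | 56% to 76% | +14 to −6 | 14.2 | 0.99 |

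The last row in patients, per sequence: 28 responders among 40 assessed is 70%. With 50 dosed, the bounds are 28/50 = 56% and (28 + 10)/50 = 76%.

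The largest possible error equals the sampling half-width when 0.70m = 1.96 × √(0.21 / (50(1 − m))), that is at m of about 20.3%. The error is zero when q = 0.70. One excluded patient in 50 (m = 0.02) moves the rate by at most 0.02 × 0.70 = 1.4 points up or 0.02 × 0.30 = 0.6 points down.

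**3-month rate.** No figure is attached, because the plan gives neither an expected 3-month rate nor the number of patients likely to miss week 6 and return at 3 months. The argument rests on the text: the analysis set depends on week 6, the endpoint is measured at 3 months, and the 3-month visit is for all patients. FAS patients with no 3-month assessment also leave that rate, through the non-missing denominator.

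**The case against.** The strongest reply is that few patients will be affected. Visits are weekly, there is a planned contact at the primary time point ("At 6 weeks after switching, patients will be asked whether they prefer to continue treatment with rhTPO or eltrombopag"), and counts continue weekly after the second drug is stopped. This stands in part: stopping treatment does not by itself remove a patient, and these features favour a low *m*. They do not cover loss to follow-up, death, withdrawal or a missed visit, and the plan itself budgets for drop-out.

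A second reply is that the FAS and SS sizes together give the number unassessed, so a reader could form the bounds. That is true if both sizes are reported by sequence. The plan does not commit to this, nor to reasons or bounds, and set sizes would not recover the discarded 3-month outcomes.

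A third reply is that counting missing as non-response could do more harm than the present rule. This stands. The error of that figure is −mq, which exceeds m(0.70 − q) in size whenever q is above 0.35. At q = 0.70 and m = 20% the observed-case rate is exact, and the non-response figure is 14 points too low. It belongs in the report as a bound and need not be the headline.

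A reader might also infer that the 4-weekly counts allowed for stable eltrombopag patients (Table 1, note b) push responders out of the FAS. The documents do not show this. No week-6 window is stated, weekly counts resume during dose adjustment, and with the ±3-day visit tolerance a day-35 count may fall on day 38, within 4 days of day 42. Nor is the inclusion criterion on 6 weeks of available follow-up shown to select on the future. Patients enrol at the switch, so its natural reading is expected availability.

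**Conclusion.** The concern holds as a stated rule with an avoidable consequence: the efficacy set is conditioned on the primary outcome having been observed, and nothing in the plan shows how much that matters. It should be fixed.

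The size is modest at low loss, at most 3.5 points with 5% unassessed. It matches sampling error only at about 20% unassessed. That outer case rests on an assumption the plan does not state, namely that all drop-out is of dosed patients and precedes week 6.

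A reader might infer that the planned rate is inflated. The documents do not support that, because the response of unassessed patients is unknown and the error can go either way. A reader might also take 20% as the expected loss from the primary rate. The drop-out figure in the sample size rationale is not tied to week 6 and does not say that.

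The loss of known 3-month outcomes does not depend on *q*. It follows from the definition for any patient seen at 3 months but not assessed at 6 weeks. How many there will be is not known.

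**What to change.** 1. Define the FAS as all patients with at least one dose of the second TPO-RA, which is the Safety Set population.
2. For each sequence, report the 6-week rate among assessed patients together with both bounds on all dosed patients: all missing as non-response, and all missing as response. State in advance which figure is the headline; that is the sponsor's choice.
3. Report the number of missing 6-week assessments and the reasons, by sequence.
4. Analyse the 3-month rate and the time-to-event endpoints on all dosed patients, whether or not they were assessed at week 6.

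The cost is wording in the analysis-set section and a few extra table rows. No visits or patients are added. The downside is a visible range around the reported rate.

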Trial Design	
This is a prospective and retrospective observational study of switching eltrombopag and rh-TPO in Chinese adult patients with primary immune thrombocytopenia. A schematic illustration of the study design is shown as follows:
 
 
 
The study includes two stages: the retrospective stage and the prospective stage. Primary ITP patients who failed initial glucocorticosteroid treatment and receive rh-TPO and then switch to eltrombopag or vice versa will be screened for eligibility. Medical records will be retrospectively reviewed to collect baseline data before 1st TPO-RA administration, information on the 1st TPO-RA, as well as the reason for switch. Patients who meet the eligibility criteria upon medical history review and clinical evaluation will be enrolled at the time of switch. The switch procedure is as per physician preference and clinical practice.
 
After enrollment, patients will be followed up prospectively on administering the 2nd TPO-RA. Both rh-TPO and eltrombopag are applied according to the approved label and clinical practice, in considering the actual condition of a patient. For patients who switch from rhTPO to eltrombopag, platelet counts will be obtained weekly under stable dose and monthly following establishment of a stable platelet count ($\geq 50*10^9/L$ for at least 4 weeks), while platelet counts will be obtained at least once a week during dose adjustment. Liver function tests (ALT, AST, TB) will be performed monthly under stable dose but increased to bi-weekly during dose adjustment. For patients who switch from eltrombopag to rhTPO, platelet counts will be obtained every other day during initial treatment and weekly during maintenance therapy.
 
Platelet counts will be obtained at least once a week for all patients who suspend/stop their 2nd TPO-RA, while liver function tests will be performed bi-weekly in patients who suspend/stop eltrombopag as their 2nd TPO-RA. Once treatment is resumed, monitoring of platelet counts and liver function will be performed as per during treatment administration. An end-of-study visit will be performed for all patients at

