Bone marrow aspirate	As clinically required.						
Pregnancy test	X						X
Concomitant therapy ^f	X	X				X	X
AE/SAE assessment	X	X				X	X

- a. For patients who switch from eltrombopag to rhTPO, CBC should be performed every other day during initial treatment and weekly during maintenance therapy.
- b. For patients who switch from rhTPO to eltrombopag, CBC should be monitored weekly until stable platelet count is observed ($\geq 50*10^9/L$ for at least 4 weeks), then CBC will be monitored every 4 weeks. Platelet counts will be obtained at least once a week during dose adjustment.
- c. For patients who switch from rhTPO to eltrombopag, liver function tests (ALT, AST, TB) will be performed every 4 weeks under stable dose but increased to every 2 weeks during dose adjustment.
- d. For patients who switch from rhTPO to eltrombopag, liver function tests (ALT, AST, TB) will be performed every 2 weeks after treatment suspension/stop.
- e. The frequency of platelet monitoring can be increased to twice weekly for patients who suspend/stop eltrombopag due to platelet counts $>250*10^9/L$.
- f. Record concomitant ITP treatment (including rescue medications), anticoagulants, and NSAIDs.

Table 2 Dose Adjustment Guidelines of Eltrombopag

After initiating eltrombopag, the dose should be adjusted to achieve and maintain a platelet count $\geq 50*10^9/L$ as necessary to reduce the risk of bleeding. A daily dose of 75 mg must not be exceeded.

Clinical haematology and liver tests should be monitored regularly throughout therapy with eltrombopag and the dose regimen of eltrombopag modified based on platelet counts as outlined in **Table 2**.

During therapy with eltrombopag, platelet counts should be assessed weekly until a stable platelet count ($\geq 50*10^9/L$ for at least 4 weeks) has been achieved. Platelet counts should be obtained monthly thereafter.

Platelet count	Dosage adjustment or response
$<50*10^9/L$ following at least 2 weeks of therapy	Increase daily dose as per 25mg. Monitor platelet count at least once a week, wait for 2 weeks, assess the treatment effect after dose increase, and consider whether further dose adjustment is needed. Maximum daily dose is 75mg per day.
$\geq 50*10^9/L$ to $\leq 150*10^9/L$	Use lowest dose of eltrombopag and/or concomitant ITP treatment to maintain platelet counts that avoid or reduce bleeding.

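### No platelet count is required at week 6, so early-stable rhTPO-to-eltrombopag patients can miss the primary assessment and drop out of the full analysis set

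*Combined protocol and SAP*

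**What the plan says.** **Endpoint.** In Endpoints, "The rate of response at 6 weeks includes the total proportion of patients who achieved CR and R at 6 weeks" in each switch sequence. CR and R each need a platelet count and no bleeding. No response means a count below 30×10⁹/L, "or less than doubling of the baseline count, or bleeding". Trial Design has response followed over the 3-month observation period, "with response at 6 weeks being the primary evaluation".

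**Counts, rhTPO to eltrombopag.** Table 1, footnote b, sets weekly CBC until the count has been at least 50×10⁹/L for at least 4 weeks; "then CBC will be monitored every 4 weeks". Trial Design says the same: "platelet counts will be obtained weekly under stable dose and monthly following establishment of a stable platelet count". So does the text introducing Table 2: "During therapy with eltrombopag, platelet counts should be assessed weekly until a stable platelet count" is reached, and "Platelet counts should be obtained monthly thereafter". Counts go back to at least weekly around a dose adjustment or when the drug is suspended or stopped.

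**Counts, eltrombopag to rhTPO.** Footnote a: "CBC should be performed every other day during initial treatment and weekly during maintenance therapy". There is no step-down.

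**Visits.** Table 1 has on-treatment columns for every 1, 2, 4 and 8 weeks and an end-of-study visit at 12 weeks ±7 d. It has no week-6 column and no week-6 window. Bleeding assessment is weekly without step-down. Endpoints asks patients and physicians for their preference at 6 weeks, and physicians are to weigh response.

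**Analysis.** Under Statistical Analysis, the FAS takes patients with at least one dose of the second drug and a 6-week response assessment. All efficacy analysis uses the FAS, and percentages are based on non-missing data by default. No other rule covers a missing response.

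**The concern.** The schedule can skip the primary time point for one group, in one sequence, chosen by its early platelet counts. The analysis rules then turn the missing count into exclusion.

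The loss would not be random. A stepped-down patient who bleeds at week 6 is a non-responder without any count and can stay in the analysis. A stepped-down patient who does not bleed cannot be classed and leaves. Because every efficacy analysis uses the FAS, that patient also leaves the 3-month response rate, although a 12-week CBC is scheduled.

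Such patients are plausible. The plan admits switches for preference or adverse events. It also describes rhTPO maintenance, entered at counts of 50×10⁹/L or more, so some patients may switch at or above that level. These patients also inform the response-maintained endpoint and the analyses by reason for switching.

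**Working it through.** The plan gives no figure for week-6 completeness, so there is nothing to reproduce. The check has two parts.

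**1. Which patients have no count near day 42?**

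Inputs from Table 1: weekly visits ±3 d, 4-weekly visits ±4 d, step-down after at least 4 weeks at 50×10⁹/L or more. Assumptions: visit deviations are uniform over whole days, and there is no dose change or suspension. The visit in week k falls on day 7k + j, with j from −3 to 3. The next count after step-down comes 28 ± 4 d later.

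The plan does not say how the 4 weeks are counted, so several readings were run. The plan also gives no week-6 window, so two were tried.

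| Reading of the 4 weeks | First count ≥50 | No count, day 42 ±3 | No count, day 42 ±7 |
|---|---|---|---|
| 28 elapsed days, clock starts at the switch | at switch | 100% | 75.5% |
| 28 elapsed days, clock starts on treatment | week 1 | 57% | 12% |
| Nominal 4 weeks | week 1 | 100% | 43% |
| Four consecutive weekly counts | week 1 | 100% | 98% |
| Four consecutive weekly counts | week 2 | 100% | 43% |

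In the ±3 d window the loss is 0% from week 2 under the second and third readings, and 0% from week 3 under the last.

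The strictest reading can be checked by hand. A patient first at 50 or above at week 1 steps down at week 5 if (35 + j₅) − (7 + j₁) ≥ 28, that is j₅ ≥ j₁. Of the 49 equally likely pairs, 28 satisfy this: 28/49 = 57%. The week-5 count is then on day 38 at the latest, outside days 39–45, and the next is past day 45. For the ±7 d window the week-5 count must also fall before day 35 (j₅ < 0), which leaves 1 + 2 + 3 = 6 pairs: 6/49 = 12%.

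With the clock starting at the switch and a ±7 d window, step-down at week 4 needs j₄ ≥ 0 (4/7). Otherwise it comes at week 5, and that count is before day 35 with probability 3/7. So 4/7 + (3/7)(3/7) = 37/49 = 75.5%.

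**2. What would the loss do to the rate?**

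The 70% rate and about 50 patients per sequence come from Sample Size Justification. The losses are assumptions, because the documents give none.

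- *Only responders lost.* With true rate p and a share f of responders lost, the observed rate is p(1 − f)/(1 − pf). For p = 0.70 and f = 0.1, 0.2, 0.3: 31.5/46.5 = 68%, 28/43 = 65%, 24.5/39.5 = 62%.
- *Mixed loss of 7 of 50, share r of them responders.* The observed rate is (35 − 7r)/43: 65% at r = 1, 67% at 0.9, 70% at 0.7, 73% at 0.5. The rate reads low if more than 70% of those lost are responders and high if fewer are.
- *Same loss, missing counted as non-response.* (35 − 7r)/50: 56%, 57%, 60%, 63%.
- *Week-6 count in place, m of 50 still missing at random, counted as non-response.* 0.70(50 − m)/50: 69% for m = 1, 67% for m = 2.

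For scale, the 95% Wilson interval for 35/50 is 56% to 81%, a half-width of about 12 points.

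**The case against.** The best defence is that week 6 is clearly meant to be assessed. It is named as the primary evaluation, a preference that weighs response is collected then, and weekly bleeding assessment puts the patient in front of the site. Footnote b does not forbid an extra count. On this view the plan lacks only a cross-reference, and actual loss is conjecture. That stands in part: sites may well take the count, so loss is possible and not certain. But no passage requires it for a stepped-down patient, and three passages describe a schedule without it.

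The affected group is also narrow: one sequence, early stable counts, still on treatment, no recent dose change. Counts above 150×10⁹/L lead to dose reduction and renewed weekly monitoring. Starting the clock at the switch fits less well with the Table 2 text, which speaks of counts during eltrombopag therapy. All this stands. Yet each reading checked still leaves some patients uncovered.

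The percentages depend on a window the plan does not state, and at ±7 d several of them fall a good deal. The loss sizes are hypothetical, and the shifts they produce among assessed patients lie inside the sampling half-width. That also stands, so no direction or size is claimed. If the baseline is the count at the switch, a patient who starts at 50 or above and stays below 100×10⁹/L has not doubled and is a non-responder; losing such patients would push the rate up.

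Finally, an FAS that requires the outcome is a wider weakness, affecting any missing week-6 response in either sequence. True, but it is what makes a missed count an exclusion here, so the two need repair together.

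**Conclusion.** The concern holds. As written, the plan does not secure the platelet count its primary endpoint needs for early-stable patients in the rhTPO-to-eltrombopag sequence, and the FAS rule removes those who cannot be classed from both the 6-week and the 3-month rates.

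That the schedule has this gap is certain from the text. Its effect is not: the documents do not say how many patients reach step-down before week 6, and the bias could go either way. The percentages in the table rest on uniform visit deviations and no dose change; the rates rest on a true 70% and assumed losses. The study's purpose is to describe this rate, and closing the gap costs little, so it should be fixed.

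**What to change.** 1. Add a CBC at week 6 (±3 d) to Table 1 for every patient in both sequences, whatever the stability of the count. It can be done at the contact already needed for the preference questions. The weekly bleeding assessment supplies the other component of response.
2. State the week-6 analysis window: the count nearest day 42, with a prespecified fallback range.
3. Define the FAS as all patients who receive at least one dose of the second drug. Keep those without a week-6 assessment in the primary denominator by a stated rule, for example as non-responders, and report an observed-case sensitivity analysis.

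Items 1 and 3 belong together. In the 7-of-50 illustration, counting missing patients as non-responders without the extra count would always fall below the true 70%.

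The cost is one blood count for each affected eltrombopag patient, SAP wording, and a rate about 1 to 3 points lower if 1 or 2 of 50 are still missing and counted as non-responders.
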